5.2.2. Primary Efficacy Analysis

The number and percentage of subjects with CIS or CIS plus papillary disease who have a complete response will be summarized separately by cohort (Cohort 1 or Cohort 2) and overall (Cohort 1 + Cohort 2) at each assessment. Ninety-five percent (95%) confidence intervals around the complete response rate at each assessment will be calculated using the Clopper-Pearson method.

The calculations of the lower (P_L) and upper (P_U) confidence limits using the Clopper-Pearson method are below:

$$P_L = \left(1 + \frac{n - n_1 + 1}{n F(1 - \alpha, 2n, 2(2 - n) + 1)}\right)^{-1}$$
$$P_U = \left(1 + \frac{n - n_1}{(n_1 + 1)F(\frac{\alpha}{2}, 2(n_1 + 1), 2n - n_1)}\right)^{-1}$$

Where

n = the number of subjects with CIS or CIS plus papillary disease

n_1 = the number of subjects with CIS or CIS plus papillary disease who have a complete response

$F(\alpha, b, c)$ is the α th percentile of the F distribution with b and c degrees of freedom.

Duration of response will be estimated (Kaplan-Meier Estimate) for those subjects who experience a complete response. Subjects who do not experience treatment failure or death will be censored at the time of the last non-missing response assessment.

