## 17 STATISTICS

### 17.1 General Principles of Statistical Analysis

The type I (alpha error) for all hypothesis testing will be set at 0.05, and all statistical tests will be two-sided. All confidence intervals will be two-sided 95% confidence intervals. Data will be summarized by reporting the frequency and percentage of subjects in each category for categorical and ordinal measures, and means, standard deviations (SD), medians, minimum and maximum for continuous measures.

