5. STATISTICAL METHODS

Descriptive statistical methods will be used to summarize the data from this study, with hypothesis testing performed for the primary and other selected efficacy endpoints. Unless stated otherwise, the term “descriptive statistics” refers to number of subjects (n), mean, median, standard deviation (SD), minimum, and maximum for continuous data and frequencies and percentages for categorical data.

All data collected during the study will be included in data listings. Unless otherwise noted, the data will be sorted first by subject number and then by phase (induction, maintenance), cycle/visit, and date.

Unless otherwise specified, all statistical testing will be two-sided, and will be performed using a significance (alpha) level of 0.05.

The statistical analyses will be conducted with the SAS® software package version 9.2 or higher. All analyses will be subject to formal verification procedures. Specifically, results will be verified utilizing independent programming prior to issuance of the draft statistical report. All documents will be verified by the lead statistician to ensure accuracy and consistency of analyses.

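### The Clopper-Pearson formulas in SAP 5.2.2, with F defined as a percentile, put each limit on the wrong side of the estimated complete response rate

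*SAP*

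**What the plan says.** SAP 5.2.2 states that 95% "confidence intervals around the complete response rate at each assessment will be calculated using the Clopper-Pearson method", by cohort and for Cohorts 1 and 2 together. It then gives explicit formulas.

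- The fraction inside the lower limit P_L reads "n - n_1 + 1}{n F(1 - \alpha, 2n, 2(2 - n) + 1".
- The fraction inside the upper limit P_U reads "n - n_1}{(n_1 + 1)F(\frac{\alpha}{2}, 2(n_1 + 1), 2n - n_1".
- The key defines n ("n = the number of subjects with CIS or CIS plus papillary disease") and n1 (the complete responders among them). It describes F(alpha, b, c) as the alpha "th percentile of the F distribution with b and c degrees of freedom".

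The level is set elsewhere. In SAP section 5, "all statistical testing will be two-sided, and will be performed using a significance (alpha) level of 0.05". In protocol 17.1, "All confidence intervals will be two-sided 95% confidence intervals". The protocol (17.5) names Clopper-Pearson but gives no formula. SAP section 1 says that the SAP prevails over the protocol where they differ, so SAP 5.2.2 holds the only written formula.

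**The concern.** A percentile is counted from the lower end of the distribution. A lower confidence limit built from F needs a low percentile (alpha/2), and an upper limit needs a high one (1 - alpha/2). The SAP has them the other way round: 1 - alpha in P_L and alpha/2 in P_U.

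The interval is the only inferential output that SAP 5.2.2 specifies for the CR rate, and it is repeated at each assessment. SAP section 5 also requires results to be verified by independent programming. One programmer coding the formula and another calling a standard exact routine would not agree.

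**Working it through.** **Inputs.** Alpha is 0.05, two-sided (SAP section 5; protocol 17.1). The method is Clopper-Pearson (SAP 5.2.2). The planning size is n = 77 (SAP 3.1). The count n1 = 24 is an illustration near the planning rate of 30%: 24/77 = 31.2%.

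**Step 1. The plan's own figures under the correct method.** The Clopper-Pearson lower limit is the alpha/2 quantile of a Beta(x, N - x + 1) distribution. At x = 0.30N:

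| N | SAP 3.1 | Recomputed |
|---|---|---|
| 121 | 0.220 | 0.2201 |
| 95 | 0.210 | 0.2102 |
| 76 | 0.200 | 0.2002 |

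The sample-size table is right, so the fault is confined to the formulas in 5.2.2.

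**Step 2. The correct interval at 24/77, with F(p; b, c) the lower percentile.**

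- P_L = [1 + (n - n1 + 1)/(n1 F(alpha/2; 2n1, 2(n - n1 + 1)))]^-1. Here F(0.025; 48, 108) = 0.6015, so P_L = 1/(1 + 54/(24 x 0.6015)) = 21.1%.
- P_U = [1 + (n - n1)/((n1 + 1) F(1 - alpha/2; 2(n1 + 1), 2(n - n1)))]^-1. Here F(0.975; 50, 106) = 1.5826, so P_U = 1/(1 + 53/(25 x 1.5826)) = 42.7%.

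Both equal the Beta-quantile limits.

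**Step 3. The formulas as they read in the available text.**

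- P_L: the second degrees of freedom are 2(2 - 77) + 1 = -149, so F does not exist. The expression is negative for every n above 2.
- P_U: the second degrees of freedom are 2 x 77 - 24 = 130. F(0.025; 50, 130) = 0.6128, so P_U = 1/(1 + 53/(25 x 0.6128)) = 22.4%, below the estimate of 31.2%.

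**Step 4. The same formulas with every doubtful character restored.** Put n1 for n, 2(n - n1 + 1) and 2(n - n1) for the second degrees of freedom, and 1 - alpha/2 for 1 - alpha. Keep the SAP's definition of F.

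- P_L: F(0.975; 48, 108) = 1.5881, so P_L = 1/(1 + 54/(24 x 1.5881)) = 41.4%.
- P_U: F(0.025; 50, 106) = 0.6060, so P_U = 1/(1 + 53/(25 x 0.6060)) = 22.2%.

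The lower limit is above the estimate and the upper limit is below it. Exchanging the labels does not repair this: 22.2% to 41.4% is narrower than the correct 21.1% to 42.7%.

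**Step 5. Does it depend on the example?** For n = 40, 77, 93 and 134 (illustrative sizes), the restored P_L is above n1/n and the restored P_U is below it for every n1 from 1 to n - 1. The printed P_U is also below n1/n throughout.

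**The case against.** The strongest reply is that the equations reached this review through a PDF reader. The term 2(2 - n) + 1 looks like a damaged 2(n - n1 + 1). The n in place of n1, the 2n - n1 in place of 2(n - n1), and even 1 - alpha in place of 1 - alpha/2 could each be a lost character. That stands, and none of these is counted here as an error in the plan. With them restored and F read as an upper-tail critical value, the pair gives exactly 21.1% to 42.7% at 24/77. The author may well have had the right formula in mind.

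What this does not rescue is the definition of F. It is a sentence of ordinary text that calls F a percentile, and with it the restored formulas still fail (Step 4). Either the arguments or the definition must change.

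A reader might go further and infer that the plan would test at the wrong error rate. If F is read as upper-tail and 1 - alpha is kept, the lower tail is 5%. Then 22/77 (lower limit 20.2%) would exclude 20%, where the correct method needs 24/77, and the one-sided error at a true rate of 20% would be 4.5% rather than 1.4%. The documents do not support that inference. It needs a programmer to repair the subscripts, overrule the definition of F, keep unequal tails, and ignore the stated 95% level. It also needs a success rule at 20%. SAP 3.1 uses 20% only to justify the sample size, and for Cohort 1-type subjects, whereas the primary analysis now pools Cohorts 1 and 2.

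**Conclusion.** The point holds as a minor error of specification. Under the SAP's own definition of F, its formulas do not give the interval it names. At 24/77 they give 41.4% and 22.2% after every charitable repair, against a correct 21.1% to 42.7%. This rests on the definition of F reading in the source file as it does here.

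It does not follow that the reported interval would be wrong. Clopper-Pearson at 95% is named in both documents, the sample-size table agrees with it, and limits on the wrong side of the estimate, or a limit that cannot be computed, would be noticed at once. Nor can it be said that the source SAP contains the negative degrees of freedom or the unequal tails. Those need a look at the typeset equation.

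**What to change.** Check the typeset equations in the source file. Then do one of two things.

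1. Replace them with P_L = [1 + (n - n1 + 1)/(n1 F(alpha/2; 2n1, 2(n - n1 + 1)))]^-1 and P_U = [1 + (n - n1)/((n1 + 1) F(1 - alpha/2; 2(n1 + 1), 2(n - n1)))]^-1. State that F(p; b, c) is the lower (cumulative) p-th percentile and that alpha = 0.05. Set P_L = 0 if n1 = 0 and P_U = 1 if n1 = n.
2. Delete the formulas and keep the named exact two-sided 95% Clopper-Pearson method.

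The cost is SAP wording only. Design, data collection and sample size are unaffected.

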5.2.3. Sensitivity Assessments for the Primary Efficacy Analysis

Given that complete response is assumed in cases where there is no evidence of treatment failure, it is important to evaluate the impact, if any, of missing data on the primary efficacy analysis. To this end, a sensitivity analysis will be conducted where subjects who have a missing centrally read pathology and/or centrally read cytology at a visit where there was an abnormal cystoscopy will be imputed as a treatment failure for that visit if the subsequent visit indicates treatment failure. A second sensitivity analysis will be performed where subjects with low grade Ta are treated as a failure.

5.2.4. Additional Efficacy Endpoints

Additional efficacy endpoints include:

- Event-free survival (EFS) in all subjects
- Cystectomy-free days in all subjects
- Time to disease recurrence in papillary subjects
- Progression-free survival (PFS) in all subjects
- Overall survival (OS) in all subjects

5.2.5. Additional Efficacy Analyses

The following analyses will be conducted in the mITT population, the evaluable population, the induction phase dosing compliant population, and the study dosing compliant population.

EFS will be estimated using the method of Kaplan-Meier. Subjects without evidence of a treatment failure who are diagnosed with upper or lower urinary tract urothelial carcinoma by histology, cytology or radiographic evidence will be censored at the date of diagnosis. Subjects without evidence of a treatment failure who undergo cystectomy will be censored at the date of cystectomy. All other subjects will be censored at the time of the last assessment. The ninety-five percent (95%) confidence interval around the EFS rate at 18 months will be presented.

Time to disease recurrence will be estimated separately for each cohort using the method of Kaplan-Meier. For subjects in Cohort 3, time to disease recurrence is defined as the number of days from first dose of study treatment to the first occurrence of treatment failure. Subjects who do not experience treatment failure will be censored at the last assessment.

Cystectomy-free days, time to progression, progression-free survival, and overall survival will be estimated based on the method of Kaplan-Meier.

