### 10.5 Maintenance Phase

Disease evaluation will be performed every 13 weeks regardless of dose interruptions or delays (see [Section 14.4](#)). Cystoscopy and urine collection for cytology during the Maintenance Phase should be done at Week 26, Week 39, Week 52, Week 65, Week 78, Week 91, and Week 104, even if there are

missed doses or dosing delays. Every effort should be made to stay on this evaluation schedule, however, a window of one week before and up to 2 weeks after these time points is permitted (e.g., the Week 26 cystoscopy and urine for cytology may be performed from Week 25 to Week 28, but as close to week 26 as possible). The complete evaluation to determine disease status (e.g., repeat cytology, cystoscopy and biopsies if required) should be completed as soon as possible following the every 13-week timepoint. Vicinium dosing may continue during these disease evaluations in the Maintenance phase per investigator discretion. Vicinium treatment should not be given within 2 weeks of any biopsy/TURBT.

Other assessments during the Maintenance Phase are as follows:

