## 17.8 Sample Size and Power

Assuming the true complete response rate at 12 months is 30%, sample sizes associated with various widths of a two-sided, exact (Clopper-Pearson) 95% confidence intervals are provided in the table below:

Sample Size (N)	Target Distance from P to Lower Limit	Proportion (P)	Lower Limit
121	0.080	0.300	0.220
95	0.090	0.300	0.210
76	0.100	0.300	0.200

Under the provided assumptions, a sample size of  $\geq 77$  evaluable subjects in Cohort 1 (see [Section 10](#)) is sufficient to estimate complete response rate with an exact 95% confidence interval that excludes 0.2 (PASS 2008).

The secondary endpoint of event-free survival (EFS) will be used to assess the treatment effect in all subjects, i.e., those with CIS (with or without papillary disease) and those with papillary-only

disease. An estimate of EFS at the 18 month time-point will be calculated. The total sample size of 134 subjects will provide at least 80% power to test the null hypothesis that the event-free survival rate at 18 months is 20% versus the alternative hypothesis that the event-free survival rate at 18 months is  $\geq 30\%$ . This calculation is based on the assumptions of a nonparametric distribution for event-free survival and the length of follow-up is 24 months.

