Subjects with CIS (Cohort 1 or Cohort 2) will be considered to have a complete response if at the time of any disease status evaluation (per protocol every 13 weeks or any unscheduled evaluation) there is no evidence of high-grade disease (CIS, high-grade Ta or any grade T1 disease) or disease progression (e.g., to muscle invasive disease). Subjects whose initial diagnosis was CIS who are found to have low-grade Ta disease at the time of an evaluation must have the low-grade disease resected by TURBT. Low-grade Ta disease is not considered a treatment failure in these subjects and they may remain on study treatment following TURBT.

Date of Complete Response or Treatment Failure

Given that the cystoscopy, biopsy, and cytology assessments may be conducted on different dates, the date of complete response or treatment failure will be defined as the earliest assessment date of these assessments.

Duration of Response

Duration of Response will be analyzed for subjects with CIS with or without papillary disease (Cohort 1 + Cohort 2) who achieve complete response using a Kaplan-Meier (KM) product-limit method. It is defined as the number of days from the date of first occurrence of complete response to the date of documented treatment failure or death, whichever occurs first. Subjects who do not experience treatment failure or death will be censored at their last assessment of response.

Event

For the purposes of defining Event-Free Survival, an event is defined as treatment failure or death on or prior to treatment discontinuation. Because disease assessments are not recorded after treatment discontinuation, a death after treatment discontinuation will not be counted as an event so as not to artificially inflate EFS. Presence of upper or lower urinary tract urothelial carcinoma and having a cystectomy are not treated as events for analysis but do trigger special data handling in the event-free survival analysis.

Event-Free Survival

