EFS is defined as the interval from the date of first dose of study treatment to an event. Subjects who have a treatment failure or die following the post induction visit will be treated as having an event on the date of treatment failure or death. Subjects without evidence of a treatment failure who are diagnosed with upper or lower urinary tract urothelial carcinoma by histology, cytology or radiographic evidence will be censored at the date of diagnosis. Subjects without evidence of a treatment failure who undergo cystectomy will be censored at the date of cystectomy. All other subjects will be censored at the time of last assessment including long-term follow up.

Censoring rules for the analysis of EFS are presented in the table below.

Table: Censoring scheme for EFS

Situation	Date of Event or Censoring	Outcome
Treatment failure	Date of treatment failure	Event
Death without treatment failure and occurring prior to treatment discontinuation	Date of death	Event
Death without treatment failure and occurring after treatment discontinuation	Date of last evaluable disease assessment on or prior to treatment discontinuation ^a	Censored ^a
No baseline disease assessment	Date of first dose	Censored
No on-study disease assessments and no death	Date of first dose	Censored
No treatment failure and no death	Date of last evaluable disease assessment	Censored
New anti-cancer therapy received without treatment failure and reported prior to or on the same day as disease assessment	Date of last evaluable disease assessment on or prior to the date of initiation of subsequent therapy	Censored
Second non-NMIBC cancer reported prior to or on the same day as disease assessment	Date of last evaluable disease assessment on or prior to the date of diagnosis of non-NMIBC cancer	Censored
a This censoring rule acknowledges that disease assessments were not recorded after treatment discontinuation due to an AE.		

Cystectomy-Free Days

Cystectomy-free days is defined as the time from the date of first dose of study treatment to physical removal of the bladder. Subjects who are alive and do not have their bladder removed will be censored at the time of last contact.

Censoring rules for the analysis of cystectomy-free days are presented in the table below.

Table: Censoring scheme for Cystectomy

Situation	Date of Event or Censoring	Outcome
Cystectomy	Date of cystectomy	Event
Death without cystectomy	Date of death	Censored
No cystectomy	Date of last contact	Censored

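### The 18-month EFS rate is read inside the permitted Week 78 visit window, so in-window failures found after the cut count as event-free

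*SAP*

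**What the plan says.** SAP 3.3.7 sets the clock: "EFS is defined as the interval from the date of first dose of study treatment to an event". SAP 5.2.5 gives the estimator, "EFS will be estimated using the method of Kaplan-Meier", and says that the 95% "confidence interval around the EFS rate at 18 months will be presented". Protocol 17.8 announces the same figure ("An estimate of EFS at the 18 month time-point will be calculated"). It adds the hypothesis: null 20%, alternative at least 30%, at least 80% power with 134 subjects. SAP 3.1 repeats this.

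On visits, Protocol 10.5 says that maintenance cystoscopy and cytology "should be done at Week 26, Week 39, Week 52, Week 65, Week 78, Week 91, and Week 104", and that "a window of one week before and up to 2 weeks after these time points is permitted". Its example shows how the window is counted: the Week 26 tests "may be performed from Week 25 to Week 28, but as close to week 26 as possible". Protocol 14 repeats the rule.

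On dating, SAP 3.3.7 says that "the date of complete response or treatment failure will be defined as the earliest assessment date of these assessments". That is a real calendar date, not the nominal visit. SAP 3.3.9 (item 4) also uses the earliest observed date when results are merged into a visit.

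Neither document gives 18 months in days, moves the EFS reading past the visit window, dates failures at the nominal visit, or plans an interval-censored estimator.

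**The concern.** Treatment failures come to light mainly at the 13-weekly evaluations, so the EFS curve falls in steps around those visits. The 18-month reading should reflect what the Week 78 evaluation found. Instead it falls inside that evaluation's own window. A failure found on Day 545 lowers the 18-month rate; the same failure found on Day 555 does not. For subjects seen after the cut, the figure reports their Week 65 status.

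The SAP also treats the same visit in two ways. For response, SAP 3.3.9 assigns Days 501 to 591 to that evaluation (labelled Maintenance Month 15, that is, 15 months after the three-month induction). A CIS subject who fails on Day 555 is a treatment failure at that visit under SAP 5.2.1, yet event-free in the 18-month EFS rate.

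The trial has a single arm, and the rate is set against a fixed 20%. No control arm shares the bias and cancels it.

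**Working it through.** **The plan's own figure.** Normal test of one proportion, null variance, two-sided 0.05, n = 134, 20% versus 30%:

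power = Φ[(0.10 − 1.96·√(0.16/134)) / √(0.21/134)] = 79.3%.

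This agrees with the stated 80% to within a point. An exact binomial rule at an upper tail of 0.025 or less rejects at 37 or more event-free of 134, with upper-tail error 2.1% and power 75.5%. The documents do not state that rule; it is used here only to express the bias as an error rate.

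**Where the cut falls.**
- Week 77 opens on Day 7×76 + 1 = 533; Week 80 ends on Day 7×80 = 560. The window is 28 days.
- Week 78 itself is Days 540 to 546.
- Eighteen months = 18 × 30.4375 = 547.9, so Day 548. On the 91-day quarter in SAP section 8, it is 6 × 91 = Day 546.
- Days 549 to 560 are 12 of the 28 permitted days (43%). With a cut at Day 546 it is 14 of 28 (50%).
- Week 90 opens on Day 7×89 + 1 = 624, the first permitted day for the Week 91 evaluation.

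**Formula.** Bias = (share of Week 78 visits after the cut) × (EFS at Week 65 − EFS at Week 78).

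**Illustration.** Assume 44% event-free after induction (borrowed from the Phase 2 complete response rate, 20/45, in Protocol 7) and equal proportional loss at each of the five visits from Week 26 to Week 78.
- True 20%: retention per visit = (0.20/0.44)^(1/5) = 0.854; Week 65 EFS = 0.20/0.854 = 23.4%; drop 3.4 points.
- True 30%: retention = (0.30/0.44)^(1/5) = 0.926; Week 65 EFS = 32.4%; drop 2.4 points.

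| Share of visits after Day 548 | Bias, true 20% | Chance of 37 or more of 134, true 20% |
|---|---|---|
| 0% | 0 | 2.1% |
| 10% | +0.3 points | 2.7% |
| 25% | +0.9 points | 3.8% |
| 43% (even spread) | +1.5 points | 5.5% |

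At a true 30%, the even spread gives 2.4 × 12/28 = +1.0 point.

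**Other failure patterns, at 43% late visits.**
- If 5 to 10% of those event-free at Week 65 fail by Week 78: +0.5 to +1.0 points at a true 20%, +0.7 to +1.4 at a true 30%. The chance of wrongly excluding 20% is 2.9 to 4.0%.
- Constant hazard from first dose: Week 65 EFS = 0.20^(65/78) = 26.2%, or 0.30^(65/78) = 36.7%. The bias is +2.6 and +2.9 points, and wrong exclusion is about 10%.

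**Does a later reading cure it?** In a simulation of 400,000 subjects (constant hazard, visits uniform in the window, failures dated at detection), reading at Day 548 gave 33.1% for a true 30.0% and 22.9% for a true 19.9%. Reading at Day 561, once the window has closed, gave 30.1% and 20.0%.

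**The case against.** The strongest reply concerns size. The protocol tells sites to keep to the schedule and as close to the target week as they can, and visits in Weeks 77 and 78 are counted correctly. If every visit fell in Week 78 itself, the simulated rate would be only about 0.3 points too high. The earliest-date rule pulls a failure back before the cut when one of its tests was done earlier. The 44% is a Phase 2 response rate in CIS subjects, not a post-induction EFS in a population that includes papillary-only disease. Protocol 7 also reports that the 7 of 45 Phase 2 subjects disease-free at one year were still so at 18 to 25 months, which suggests few failures over this interval. EFS is secondary, the 95% half-width at n = 134 is about 7 to 8 points, and dating events at detection is ordinary Kaplan-Meier practice. All of this stands as a limit on size. None of it removes the mechanism or changes the direction.

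Three stronger readings are tempting, but the documents do not support them.
- A reader might assume that all Week 78 visits run late, giving +3.4 points and about a 15% chance of wrongly excluding 20%. Nothing in the documents suggests such timing.
- A reader might call this the only efficacy figure with a benchmark. The primary response rate has its own, an interval that excludes 0.2 (Protocol 17.8, SAP 3.1).
- A reader might say that the bias reflects scheduling and not the drug. The formula multiplies the late share by the Week 65 to 78 failure rate, so both matter.

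**Conclusion.** The point holds as a cheap improvement. Followed as written, with 18 months converted to days in the usual way, the plan gives an 18-month EFS rate that is biased upward relative to Week 78 status and at odds with the SAP's own response window for that visit. The direction follows from the documents; the size does not. On the illustrative assumptions, with a true rate of 20%, the bias is about +0.3 to +0.9 points with 10 to 25% late visits and about +1.5 with an even spread. Under the assumed 37-of-134 rule, the chance of wrongly excluding 20% rises from 2.1% to about 2.7 to 5.5%. The bias would be smaller if few subjects fail between Weeks 65 and 78, and larger under a constant hazard. The rate is secondary, but it is the EFS figure for which the plan states a null, an alternative and a power.

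**What to change.** In SAP 5.2.5, define the 18-month EFS rate as the Kaplan-Meier estimate at Study Day 560 (first dose = Day 1), including events on that day. Every in-window Week 78 evaluation then counts, and no in-window Week 91 evaluation can enter, since that window opens on Day 624. Show the estimate at Day 591, the end of the matching SAP 3.3.9 window, as a check for out-of-window visits.

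The cost is one sentence and one extra reading of the same curve, with no new data. The estimate becomes slightly less favourable. If most visits ran late, it could fall slightly below the true 18-month value, because failures arising between Day 548 and Day 560 would also count: in the simulation with all visits late, a true 20.0% read as 19.6% just after the window.
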